**Table 6. Post-treatment Assessments, Phase 1b and Phase 2**

Examination	Study 5F9004, Post-treatment Assessments: Phase 1b/2 Solid Tumor/CRC Trial of Hu5F9-G4 + Cetuximab			
Cycle (28-day cycles)	End of Treatment	Safety Follow-up	Long-term Follow-up	Survival Follow-up
	Within 1 Week of EOT Decision	30 Days after Last Dose of study drug	Until disease progression or new anti-cancer therapy	Up to 60 months from date of LPE
Visit Window		± 1 Week	± 2 Weeks	± 1 Month
Assessments				
Serum or urine pregnancy test		X		
CBC w differential, platelets, reticulocyte count		X		
Peripheral blood smear		X		
Serum chemistry		X		
Haptoglobin, D-Dimer, thrombin time, and plasma fibrinogen		X		
PT/INR, aPTT		X		
Pharmacokinetics	X a	X a		
Correlative studies	X		X b	
Antidrug Antibodies	X	X		
CD47 Receptor Occupancy	X c			
ECOG performance status		X		
Vital signs		X		
Physical examination (symptom directed)		X		
PPD				
Response assessment	X e	X d,e	Q8W b	
Adverse events	X	X	Q4W b	
Concomitant medications	X	X		
Survival follow-up and new anti-cancer therapy				Q3M

Abbreviations: aPTT = activated partial thromboplastin time; CBC = complete blood count; CRC = colorectal cancer; DLT = dose-limiting toxicity; ECOG = Eastern Cooperative Oncology Group; EOT = End of Treatment Visit; INR = international normalized ratio; LPE = last patient enrolled; M = month(s); PT = prothrombin time' W = week(s).

- Required only in Phase 1b.
- Details provided in [Section 7.6](#).
- Sample to be collected only if the visit occurs prior to Cycle 2. Samples are collected only for Phase 1b, Cohorts 1 to 4.
- Required only if not completed within the 4 weeks prior to the Safety Follow-up Visit.
- Details provided in [Section 10](#).

**Table 7. Pharmacokinetic Assessments, Phase 1b**

Phase 1b	Cycle 1						Cycle 2						Cycle 3		C4-C5	C7+	EOT	SFU
Day	1	8	9	11	15	22	1	2	4	8	15	22	1	8	1	1	—	—
Before cetuximab infusion (within 12 hr)		X			X	X	X						X	X	X a		X	X
Before Hu5F9-G4 infusion (within 12 hr)	X	X b			X b	X b	X b			X b	X a,b	X a	X	X				
1 hr (± 15 min) after Hu5F9-G4 infusion	X	X			X	X	X			X			X	X	X a	X a		
24 hr (± 8 hr) after Hu5F9-G4 infusion (Cycle 1 Day 8 or Cycle 2 Day 1)			X					X										
72 hr (± 12 hr) after Hu5F9-G4 infusion (Cycle 1 Day 8 or Cycle 2 Day 1)				X c					X									
1 hr (± 15 min) after cetuximab infusion		X					X						X		X a			

Abbreviations: C = cycle; EOT = End of Treatment Visit; hr = hour(s); min = minute(s); SFU = Safety Follow-up Visit.

a Starting with Cycle 5, samples to be collected every other cycle (e.g., Cycle 5, 7, 9, and so on).

b. Hu5F9-G4 sample may be collected before the cetuximab infusion at same time as “pre-cetuximab infusion” PK timepoint.

c Sample to be collected before Hu5F9-G4 dose when applicable to Loading Dose Cohort.

**Table 8. Pharmacokinetic Assessments, Phase 2**

Phase 2	Cycle 1			Cycle 2			C3	C4	C5+
Day	1	8	15	1	8	15	1	1	1
Before cetuximab infusion (within 12 hr)		X		X		X	X	X	X a
1 hr ( $\pm$ 15 min) after cetuximab infusion		X	X	X			X	X	X a
Before Hu5F9-G4 infusion (within 12 hr)	X	X b	X b	X b			X	X b	X a,b
1 hr ( $\pm$ 15 min) after Hu5F9-G4 infusion	X	X	X	X		X	X	X	X a

Abbreviations: C = cycle; hr = hour(s); min = minute(s).

Note: If at any point in the study the CTSC determines that sufficient PK data have been generated, it may halt the collection of PK samples.

- Starting with Cycle 5, samples to be collected every fourth cycle (e.g., Cycle 5, 9, 13, end of treatment, and survival follow-up).
- Hu5F9-G4 sample may be collected before the cetuximab infusion at same time as “pre-cetuximab infusion” PK timepoint.

**Table 9. Correlative Studies Sample Time Points, Phases 1b and 2**

Time Points	Cycle 1			Cycle 2	Cycle 3	EOT	LTFU
Day	1	8	15	1	1		
Phase 1b							
Pre-study drug infusion a,b	X	X	X	X	X c		
1 hour ( $\pm$ 15 min) after Hu5F9-G4 infusion	X	X	X				
Phase 2							
Pre-study drug infusion a,b	X			X	X c		
1 hour ( $\pm$ 15 min) after Hu5F9-G4 infusion	X						
Phase 1b and Phase 2						X d	X e

Abbreviations: EOT = End of Treatment Visit; LTFU = long-term follow-up; min = minute(s).

- Sample to be collected before cetuximab infusion when applicable.
- Pre-infusion laboratory tests may be collected up to 72 hours before study drug treatment.
- To be performed with response assessment ( $\pm$  1 week from Cycle 3, Day 1).
- Sample to be collected within 1 week of EOT decision.
- Obtained at the time of disease progression, or the start of a new anti-cancer therapy.

**Table 10. CD47 Receptor Occupancy Sample Time Points, Phase 1b, Cohorts 1 to 4**

Time Points	Cycle 1						Cycle 2		C3	C4+	EOT
Day	1	2	8	11	15	22	1	8	1	1	—
Pre-study drug infusion	X		X a	X b	X a	X a,c	X d				
1 hr (± 15 min) after Hu5F9-G4 infusion	X		X	X b	X	X			X	X c	
24 hr (± 8 hr) after Hu5F9-G4 infusion on Day 1		X									
72 hour (± 8 hr) after Hu5F9-G4 infusion on Day 8 e				X							

Abbreviations: C = cycle; EOT = End of Treatment Visit; hr = hour(s); min = minute(s).

- a. Sample to be collected before cetuximab infusion when applicable.
- b. Samples to be collected from patients in the loading dose cohort only.
- c. Starting with Cycle 5, samples to be collected every other cycle (e.g., Cycles 5, 7, 9, and so on).
- d. Sample to be collected only if the visit occurs prior to Cycle 2.
- e. Sample to be collected from patients in non-loading dose cohort(s) only.

## 7.2. Assessment by Study Period

### 7.2.1. Screening Assessments

The following procedures are to be completed during the Screening period:

- Confirmation that the Informed Consent Form has been signed and consent process has been documented.
- Confirmation that all inclusion/exclusion criteria have been met.
- Demographic data including sex, date of birth, age, race, and ethnicity.
- Vital signs: blood pressure, pulse, respiration, temperature, height and weight.
- Physical examination (complete) and ECOG ([Appendix C](#)).
- Visual acuity assessment by Snellen eye chart or comparable eye chart.
- Single ECG.
- Relevant medical and cancer history will be completed through consent (all findings recorded on the medical history electronic case report form [eCRF]).
- Documentation of concomitant and prior medications.
- Adverse Events related to Screening procedures and any SAEs reporting.
- Serum or urine pregnancy test (in women of childbearing potential).
- Local laboratory values, including CBC (with differential, platelets, reticulocyte count), serum chemistry, serum uric acid, phosphorous, haptoglobin, D-dimer, thrombin time, plasma fibrinogen, PT/INR, aPTT, and urinalysis. (See .)
- Local laboratory Type and Screen (ABO/Rh) and DAT. (Details are provided in [Section 7.3.4](#)).
- Local laboratory Peripheral Blood Smears. (Details are provided in [Section 7.3.5](#)).
- ECOG performance status.
- Tumor biopsy (within 2 weeks prior to first dose of drug): strongly encouraged for Phase 1b, mandatory for Phase 2. Archival tumor tissue may be collected by the sponsor for correlative studies. The tissue block is preferred, but if not available at least 10 unstained slides are suggested.
- Response assessment: diagnostic imaging. (Historic imaging may be used for

screening if performed within 30 days of the first dose of Hu5F9-G4; details are provided in [Section 10](#)).

- Tumor molecular profile if available including: Microsatellite Instability status (MSI-High, MSI-Low, MSI-Stable, or unknown), Primary tumor sidedness (Left, Right, or unknown), BRAF V600E mutation (Yes, no, or unknown), KRAS mutation status (wild-type, mutant or unknown), NRAS status (wild-type, mutant, or unknown), PIK3CA mutation analysis (yes, no, or unknown).

Screening assessments will be completed within a 30-day Screening period prior to the enrollment. Screening assessments may be repeated during the 30-day Screening period. Screening assessments may be used for Cycle 1, Day 1 dosing if performed within 72 hours of study drug administration. Assessments performed as part of standard of care prior to ICF may be used if they are within the 30-day Screening period.

### **7.3. Description of Study Procedures**

Refer to SOA [Table 4](#) through for timing of study procedures.

#### **7.3.1. Physical Examination/Visual Acuity**

Complete physical exam should be performed at Screening. Thereafter, symptom-directed physical exams are acceptable and may also include routine examination of the skin (including fingers, toes, and ears) and CNS. For patients who have a change in visual acuity of 3 lines or more on a Snellen chart or comparable eye chart, an ophthalmologist should be consulted for additional evaluation.

#### **7.3.2. Vital Signs**

Vital signs should include heart rate, respiratory rate, blood pressure, temperature, and weight. Height should be recorded during Screening only. Weight should be recorded during Screening and on Day 1 of each cycle.

### **7.3.3.     Electrocardiographs**

One ECG will be performed at screening. Triplicate ECGs will be performed before the cetuximab dose (within 2 hours of infusion) and within 30 minutes of the end of Hu5F9-G4 infusion for Phase 1b only.

### **7.3.4.     Type and Screen (ABO/Rh), DAT**

Due to the risk of developing anemia, blood phenotyping, type and screen (ABO/Rh), and direct antiglobulin test (DAT) should be performed at Screening prior to exposure to Hu5F9-G4: Full phenotyping (if not transfused in last 3 months) – ABO, Rh, D, C, E, Kell, Kidd, Duffy, MNS, and antibody screen. Treatment with Hu5F9-G4 may make phenotyping difficult due to expected coating of the RBC membrane. In addition, patients who experience a drop in hemoglobin to below 9 g/dL at any time, or patients in whom clinical findings indicate a possible need for transfusions, it is recommended, but not required, that a Type and Screen and DAT be performed. Details are provided in [Table 11](#).

### **7.3.5.     Peripheral Blood Smear Assessment**

Peripheral smears will be collected prior to selected study drug infusions and assessed for the presence of hemagglutination, in addition to standard cell morphology assessment. Slides should be processed and assessments should occur in accordance with the local laboratory's standard reporting timelines. These samples should be collected from the arm contralateral to the arm being used for drug infusion, if possible. Peripheral smears will be evaluated according to the guidelines provided in [Appendix E](#). For patients undergoing blood transfusion, samples for peripheral smears will be collected 1 hour ( $\pm$  30 minutes) after completion of the transfusion. [PPD](#) [REDACTED]  
[REDACTED]  
[REDACTED].

### **7.3.6.      Pregnancy Test**

Pregnancy tests are required only for women of childbearing potential (excluding patients who are post-menopausal with absence of menses for at least 1 year and/or surgically sterilized). A urine or serum pregnancy test is required at Screening and within 72 hours prior to dosing on Day 1. The Day 1 pregnancy test does not need to be repeated if the Screening pregnancy test was done within the 72 hours prior to dosing. Pregnancy tests will be obtained every 8 weeks.

### **7.3.7.      Adverse Events**

At each visit all AEs observed by the Investigator or reported by the patient that occur after the first dose of study drugs through 30 days after the last dose of study drugs are to be reported using the applicable electronic case report form (eCRF; [Section 9.3.1](#)). AEs that occur prior to assignment of study treatment that are assessed as related to a protocol-mandated intervention (e.g., invasive procedures such as biopsies) must also be reported.

Following 30 days after the last dose of investigational product, Investigators should report any SAEs they assess as related to Hu5F9-G4 or cetuximab.

### **7.3.8.      Concomitant Medications**

All concomitant medications taken by a patient while on study are to be documented. Changes in baseline concomitant medication information is to be collected after consent through the end of the 30-day Safety Follow-up Period. Concomitant medications associated with procedure-related AEs will be captured from the time of informed consent on. Information to be collected includes therapy name, indication, dose, unit, frequency, route, start date, and stop date, and is to be reported using the applicable electronic case report form (eCRF).

## **7.4.      End of Treatment Visit**

End of Treatment Visit to be completed within 1 week of the decision to end treatment with Hu5F9-G4.

- Pharmacokinetic sample collection (for Phase 1b only). PK samples will be collected for Hu5F9-G4 and cetuximab.
- Correlative Studies
- Antidrug Antibodies
- CD47 Receptor Occupancy (only if End of Treatment Visit occurs prior to Cycle 2).
- Response Assessment, if not performed within the last 4 weeks. (Details are provided in [Section 10](#))
- Adverse Events
- Concomitant medications

### **7.5. Safety Follow-up Visit**

Safety Follow-up visit to be completed within 30 days ( $\pm$  1 week) after the last dose of Hu5F9-G4.

- Local Laboratory
  - CBC (w differential, platelets, reticulocyte count)
  - Serum chemistry
  - Haptoglobin, D-Dimer, thrombin time, and plasma fibrinogen
  - PT/INR, aPTT
- Local laboratory Peripheral Blood Smear
- Serum or urine pregnancy test (in women of childbearing potential)
- Pharmacokinetic sample collection for Hu5F9-G4 and cetuximab
- Antidrug Antibodies
- ECOG performance status [Appendix C](#)
- Vital signs
  - blood pressure
  - pulse
  - respiration
  - temperature
  - weight

- Adverse Events
- Concomitant medications
- Physical examination (symptom-directed)
- Response Assessment ( $\pm$  1 week), if not performed within the last 4 weeks  
([Section 10](#))

## 7.6. Long-term Follow-up

Patient will be followed until disease progression or until they begin a new anti-cancer therapy.

- Response assessment ( $\pm$  1 week), every 8 weeks (Section 10)
- Correlative studies

For patients who achieve a partial or complete response while on study, a repeat disease assessment will be obtained at the time of disease progression whenever possible. These assessments include:

- Blood sample for correlative studies
- PPD

Following the Safety Follow-up Visit, patients with ongoing drug-related AEs and SAEs will be followed for safety. If any study drug-related AEs or SAEs are ongoing after the Safety Follow-up Visit, follow-up with the patient will occur at least every 4 weeks until resolution to baseline or stabilization of these events, unless the patient starts another anti-cancer therapy. Follow-up will stop when a patient begins another anti-cancer therapy.

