### **3.9. Estimated Study Duration**

It is anticipated that this study will take approximately 42 months to complete.

Patient participation will include screening, treatment, and follow-up. Screening will last up to 30 days before first dose of study drugs, during which time the patient's eligibility and baseline characteristics will be determined. Treatment with study drugs may be continued until an unacceptable drug-related toxicity occurs, patient refusal, or until disease progression. Post treatment, patients will be observed for disease progression and survival until death, withdrawal of consent, or the end of the study, whichever occurs first.

Recruitment will cease when one of the following occurs:

- Study treatment is considered too toxic to continue treatment before the anticipated number of patients are recruited. This assessment will be made by the CTSC.
- The stated number of patients to be recruited is reached. This number may be increased to include replacement patients for those who are not DLT evaluable or patients in Phase 2 who are not evaluable for efficacy as defined in [Section 11](#); and patients added to intermediate dose or expanded cohorts as determined by the CTSC, and approved, if necessary, by the appropriate IRBs.

- The stated objectives of the trial are achieved.

Interim study database lock may be implemented at the discretion of the CTSC once all Phase 2 patients enrolled have achieved at least 1 tumor efficacy assessment.

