## **6.2. Post-therapy Follow-up and Patient Study Completion**

Patients who complete, terminate, or decline further treatment should be encouraged to return for an End of Treatment Visit for evaluation of safety within 1 week of the decision to end Hu5F9-G4 treatment. The studies to be performed at end of treatment are listed in the Schedules of Assessments (SOAs), [Section 7.4](#). It is strongly encouraged that patients return for their Safety Follow-up Visit 30 days ( $\pm$  1 week) after the last dose of last study drug received. The Safety Follow-up Visit assessments are described in [Section 7.5](#).

Patients are considered to have completed study drug treatment when they finish the Safety Follow-up Visit 30 days ( $\pm$  1 week) after their last dose of the last study drug received, unless they are experiencing ongoing drug-related AEs and serious adverse events (SAEs). For patients being followed for ongoing AEs or SAEs, follow-up visits will continue at least every 4 weeks until resolution to baseline or stabilization of these events, unless the patient starts another anti-cancer therapy. Follow-up for ongoing AEs or SAEs after the Safety Follow-up Visit will stop if a patient begins another anti-cancer therapy.

All patients, including those who discontinue study treatment early, will be followed for response until progression and for survival for 5 years from the date of enrollment. For any patient who dies during this period, the cause of death must be reported to the Sponsor. Patients are considered to have completed study participation when they are no longer followed for disease progression or survival.

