## 7.7. Survival Follow-up

All patients who permanently discontinue all study treatment for disease progression (according to the RECIST Version 1.1 Criteria; Section 10), clinical progression, unacceptable toxicity, partial withdrawal of consent, or administrative decision, will be contacted during a clinic visit or by telephone to assess survival, disease progression (if not documented previously), and the commencement of new cancer therapy following the last administration of study drugs. Patients will be contacted

every 3 months ( $\pm$  1 month) from the date of the safety follow-up visit, until 60 months from the date that the last patient is enrolled into the study or full withdrawal of consent. For any patient who dies during this period, the cause of death must be reported to the Sponsor. The patient's primary physician or family may be contacted by the investigator to obtain survival information in case the patient cannot be reached. Public records may also be used to obtain survival information if the patient cannot be reached.

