4 EFFICACY ANALYSIS

Confirmed best response based on RECIST v1.1 will be summarized for All Treated Patients with CRC by cohort for KRAS wild-type and KRAS mutant patients separately. ORR will be calculated based on All Treated Patients with measurable disease at baseline.

PFS is defined as the duration of time from dose initiation to the first date of objectively documented disease progression per RECIST v1.1 or death. Patients who do not have objectively documented disease progression and did not die will be censored at their last tumor assessment date.

OS is defined as the duration of time from dose initiation to the date of death due to any cause. Patients who did not die will be censored at their last known alive date.

Both PFS and OS will be summarized using Kaplan-Meier methods and summary statistics will include their 95% confidence intervals for All Treated Patients with CRC by cohort for KRAS wild-type and KRAS mutant patients separately.

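### The protocol gives two stopping points for response assessments, and the SAP's PFS rule credits unscanned time on a new therapy to patients who die; the survival follow-up limits also differ

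*Protocol*

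**What the plan says.** **Response follow-up.** Protocol Section 7.6 states: "Patient will be followed until disease progression or until they begin a new anti-cancer therapy". The long-term follow-up column of Table 6 agrees: "Until disease progression or new anti-cancer therapy". Section 6.2 says that all patients, including those who stop treatment early, "will be followed for response until progression and for survival for 5 years from the date of enrollment". It makes no exception for new therapy.

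**PFS.** SAP Section 4 measures PFS from dose initiation "to the first date of objectively documented disease progression per RECIST v1.1 or death". Only patients with neither event are censored, at the last tumor assessment. Protocol Section 11.3.1.4 defines the event the same way. Neither text has a rule for new anti-cancer therapy or for a death after missed scans. SAP Section 3.8 tabulates subsequent therapy but does not link it to PFS, and SAP Section 7 lists no relevant change. The note in Protocol Section 11.3.1.6 ties documented progression to PD on the overall response form.

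**Survival follow-up.** Section 6.2 sets 5 years from each patient's own enrollment. Section 7.7 continues contacts "until 60 months from the date that the last patient is enrolled into the study or full withdrawal of consent", and Table 6 says "Up to 60 months from date of LPE". Section 3.9 adds: "It is anticipated that this study will take approximately 42 months to complete".

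**The concern.** Sites cannot follow both Section 6.2 and Section 7.6 for a patient who starts another therapy before documented progression. The choice also changes what PFS measures.

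- Under Section 6.2, scans continue after the switch. PFS then ignores the new therapy but still observes progression on it.
- Under Section 7.6, scans stop at the switch. Progression can no longer be documented by a scheduled scan, yet death stays an event whenever it comes. The patient is carried as progression-free up to death, or goes back to the last scan if alive at the cut-off.

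The second case is neither a PFS that disregards new therapy, because nobody is scanning, nor one censored at new therapy. It lengthens PFS for switchers who die. Switching before documented progression is foreseeable, since Section 7.7 lists clinical progression, toxicity and administrative decision among the reasons for stopping treatment.

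At stake are the Kaplan-Meier PFS estimates for each KRAS cohort and, to a lesser degree, the interim rule in Section 11.4. That rule closes a cohort when median PFS is no more than 2 months and ORR is below 10% in 15 patients.

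**Working it through.** **1. The plan's own figure.** The only powered figure is 44 patients per arm (ORR 5% against 15%, one-sided alpha 0.10, power 0.80). An exact single-stage binomial test with n = 44 and success at 5 or more responses has alpha 0.0675 and power 0.8097, so 44 reproduces. It rests on ORR and is untouched here. PFS has no sample-size figure to reproduce.

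**2. One patient under the written rule.**
- Last scan at week 8 without PD: 56 / 30.4375 = 1.84 months.
- New therapy at week 10. The week-8 scan is less than 4 weeks old, so no end-of-treatment scan is required.
- Death at month 9: PFS is an event at 9.0 months.
- Alive at cut-off: PFS is censored at 1.84 months.

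So 9.0 − 1.84 = 7.2 months without a scan count as progression-free only because the patient died.

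**3. Size across a cohort.** The 8-week scan interval is from Protocol Section 10.1. Everything else is assumed:
- true progression exponential, median 2 months;
- survival after progression exponential, median 4.5 months;
- cut-off at 18 months;
- a share f who switch at a uniformly random time before documented progression.

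Check of the fully scanned value: the third scan falls at 3 × 1.84 = 5.52 months, and 0.5^(5.52/2) = 0.148. The few deaths between 5.52 and 6 months bring the simulated value to 14.7%.

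Simulated Kaplan-Meier PFS at 6 months follows. In each range the lower value assumes a scan at the switch and the higher value assumes none.

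| Share switching, f | Scanned to PD | Written rule with Section 7.6 | Censored at last scan before new therapy |
|---|---|---|---|
| 5% | 14.7% | 16.0–16.7% | 14.8–15.2% |
| 10% | 14.7% | 17.3–18.7% | 15.0–15.8% |
| 20% | 14.7% | 19.6–22.7% | 15.5–17.1% |

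Repeat runs differ by about 0.2 points. At 20% the written rule adds 19.6 − 14.7 = 4.9 to 22.7 − 14.7 = 8.0 points; censoring leaves 0.8 to 2.4 points.

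The median moves only from about 3.5 to 3.7 months, because it is pinned near the second scan at 3.68 months. That depends on the assumed 2 months. In a second model (true median 1.8 months, 4.8 months from documented progression to death, no scan at the switch, all deaths observed), 10% switching moves the median from the first scan (1.84) to the second (3.68). It does so under the written and the censored rule alike.

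**4. Interim rule.** The second model with true median 1.5 months and 15 patients gives these chances that median PFS is at most 2 months:

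| f | Written rule, all deaths observed | Censored at last scan |
|---|---|---|
| 0% | 0.72 | 0.72 |
| 10% | 0.56 | 0.72 |
| 20% | 0.38 | 0.66 |
| 30% | 0.22 | 0.61 |

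The written-rule column is an extreme: at an early interim many switchers will be alive and hence censored. If none had died, the written rule would coincide with the last column. Closure also needs ORR below 10%, so these are not closure probabilities.

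**5. Survival limits.** Let accrual last A months (not given in the documents). The first patient is followed for 60 months under Section 6.2 and 60 + A under Section 7.7: 72, 78, 84 or 90 months for A = 12, 18, 24 or 30. Followed in full, both rules run to month 60 + A, which is 18 + A months beyond the anticipated 42. A 42-month study gives the last patient 42 − A months: 30, 24, 18 or 12.

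**The case against.** **Scans near the switch.** Sections 7.4, 7.9 and 10.1 call for a response assessment at end of treatment unless one was done within 4 weeks or PD was already documented, and Section 7.5 repeats the 4-week condition at safety follow-up. This stands, and is why the estimates are ranges. It does not close the gap: a scan up to 4 weeks old may stand in, and the switch can come later than the visit.

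**Progression is still asked about.** Section 7.7 contacts patients every 3 months about progression not yet documented. That softens the problem, and the simulation gives it no weight. But contact may be by telephone, no scan is required, and progression counts only as PD on the response form.

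**Switching may be rare.** Treatment runs until progression, toxicity or refusal, and Section 10.2.2 lets it continue past RECIST progression. The share is unknown; at 2% the excess is under 1 point.

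**The written PFS rule is legitimate.** Counting progression or death regardless of new therapy is an accepted definition, and censoring at new therapy is informative if patients switch because they are worsening. In the table the censored estimate is still above the fully scanned one. So the choice of primary rule is open. What does not stand is pairing the written rule, unexamined, with scans that stop at the switch.

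**Stronger readings.** A reader might infer that OS follow-up and the end of study are undefined. They are not: SAP Section 4 censors OS at the last known alive date, and Protocol Section 6.3 ends the study when follow-up is complete or the steering committee decides. A reader might also take 42 months as a third follow-up limit, but Section 3.9 gives it as an anticipated duration. Nor do the documents plan a claim of durable benefit from the PFS tail: analyses are descriptive and the SAP does no formal testing.

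**Conclusion.** The point holds as a conflict in current text with a modest, conditional effect. Section 6.2 disagrees with Section 7.6 and Table 6 on when response assessments end, and SAP Section 4 does not settle how PFS treats the patients affected. Following Section 7.6 biases PFS upward relative to scanning everyone to progression. Under the stated assumptions the excess in 6-month PFS is about 5 to 8 points at 20% switching and 1.3 to 2.0 points at 5%, with a median shift of about 0.2 months. The switching share, both medians and the cut-off are assumptions, so direction is better supported than size. The primary ORR analysis and the 44 per arm are unaffected. The interim rule could be affected, by an amount the documents do not allow one to fix.

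The survival conflict is one of anchor: own enrollment in Section 6.2 against last patient enrolled in Section 7.7 and Table 6. It changes how long earlier patients are followed, not how OS is defined. The anticipated 42 months fits neither rule carried through in full.

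**What to change.** 1. State one response follow-up rule, in the same words, in Protocol Sections 6.2 and 7.6 and Table 6.
2. If scans stop at new therapy, add to SAP Section 4 a PFS analysis censored at the last tumor assessment before new anti-cancer therapy. Report it beside the present rule, and state in advance which is primary and which one feeds the interim median. Report the number of patients who switch without documented PD, so that the size of the issue is visible.
3. State one survival follow-up limit in Sections 6.2 and 7.7 and Table 6, and align the anticipated duration in Section 3.9 with it.

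The cost is wording in both documents and one extra Kaplan-Meier table per cohort. The downsides are fewer PFS events and possibly informative censoring in the added analysis, and a slightly less favorable PFS tail.
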